8.4 COMPLIANCE WITH TRIAL REGISTRATION AND RESULTS POSTING REQUIREMENTS

Under the terms of the Food and Drug Administration Modernization Act (FDAMA) and the Food and Drug Administration Amendments Act (FDAAA), the Sponsor of the trial is solely responsible for determining whether the trial and its results are subject to the requirements for submission to the Clinical Trials Data Bank, <http://www.clinicaltrials.gov>. Information posted will allow subjects to identify potentially appropriate trials for their disease conditions and pursue participation by calling a central contact number for further information on appropriate trial locations and trial site contact information.

9 ETHICAL CONSIDERATIONS

The clinical study will be conducted in accordance with the current IRB- approved clinical protocol; ICH Guidelines on Guidelines on Good Clinical Practice; and relevant policies, requirements, and regulations of the University of Texas MD Anderson Cancer Center IRB, and applicable federal agencies.

9.1 INFORMED CONSENT

The investigator (i.e., the study site principal investigator) will make certain that an appropriate informed consent process is in place to ensure that potential research subjects, or their authorized representatives, are fully informed about the nature and objectives of the clinical study, the potential risks and benefits of study participation, and their rights as research subjects. The investigator, or a sub-investigator(s) designated by the MD Anderson IND Office, will obtain the written, signed informed consent of each subject, or the subject's authorized representative, prior to performing any study-specific procedures on the subject. The date and time that the subject, or the subject's authorized representative, signs the informed consent form and a narrative of the issues discussed during the informed consent process will be documented in the subject's case history. The investigator or sub-investigator will retain the original copy of the signed informed consent form, and a copy will be provided to the subject, or to the subject's authorized representative.

10 STUDY DOCUMENTATION, MONITORING, AND ADMINISTRATION

The investigator and the head of the medical institution (where applicable) agrees to allow the IND Office monitor direct access to all relevant documents and to allocate their time and the time to their staff to monitor to discuss findings and any issues.

- Monitoring visits will be conducted in a manner to ensure that the:
- Data are authentic, accurate, and complete.

Proprietary Information of MD Anderson

- Safety and rights of subjects are being protected.
- Study is conducted in accordance with the currently approved protocol and any other study agreements, ICH GCP, and all applicable regulatory requirements.

Appendix 1: Response Assessment for Neuro-Oncology (RANO)

RANO and iRANO criteria (Brain Metastases)

Brain metastases	
COMPLETE TARGET	Disappearance of all enhancing target and non-lesions for ≥ 4 weeks; no new lesions; no steroids; clinically stable or improved
PARTIAL RESPONSE	$\geq 30\%$ decrease in sum of longest diameters of target lesions for ≥ 4 weeks; no new lesions; stable or decreased steroid dose; clinically stable or improved
MINOR RESPONSE	NA
STABLE DISEASE	Does not qualify for complete response, partial response, or progressive disease
PROGRESSIVE DISEASE	$\geq 20\%$ increase in the sum of longest diameters of target lesions; or unequivocal progression of enhancing non-target lesions; or new lesions; or substantial clinical decline
The iRANO criteria integrate into the existing RANO criteria for malignant glioma, low-grade glioma, and brain metastases by providing recommendations for the interpretation of progressive imaging changes. Specifically, iRANO recommends confirmation of disease progression on follow-up imaging 3 months after initial radiographic progression if there is no new or substantially worsened neurological deficits that are not due to comorbid events or concurrent medication, and it is 6 months or less from starting immunotherapy. If follow-up imaging confirms disease progression, the date of actual progression should be back-dated to the date of initial radiographic progression. The appearance of new lesions 6 months or less from the initiation of immunotherapy alone does not define progressive disease. FLAIR=fluid-attenuated inversion recovery. iRANO =immunotherapy Response Assessment in Neuro-Oncology. N/A=not applicable.	

Appendix 2: RECIST v1.1

Response Evaluation Criteria in Solid Tumors (RECIST v1.1 Criteria)

The RECIST criteria should be used to assess response to treatment. Only patients with measurable disease should be entered in the study. Measurable extracranial disease is defined as the presence of one lesion that can be accurately measured in at least one dimension (longest diameter to be recorded) as ≥ 2.0 cm with conventional techniques (or as ≥ 1.0 cm by spiral CT). Evaluable lesions should be followed for the assessment of response. Non-measurable lesions include bone lesions, ascites, pleural/pericardial effusion, lymphangitic carcinomatosis, abdominal masses that are not confirmed by CT, and cystic lesions. Disease progression and response evaluations for intracranial and extracranial disease will be determined according to the definitions established in the Response Evaluation Criteria in Solid Tumours (RECIST v1.1). Minor modifications will be applied to the assessment of intracranial lesions:

- General: target lesions should be representative of the subject's baseline tumor burden and should be selected based on their size (i.e. lesions with the longest diameter) and their suitability for accurate repeat assessment.
- Intracranial lesions: (the modifications to RECIST v1.1. impact the number and the minimal size of the target lesions selected at baseline) up to five lesions should be selected as target lesions; all brain lesions in excess of these five target lesions have to be regarded as non-target lesions. Measurable lesions are defined as those that can be accurately measured in at least one dimension with the longest diameter ≥ 5 mm when evaluated with contrast-enhanced MRI. Contrast-enhanced MRI is the only imaging modality accepted for assessment of intracranial lesions.
- Extracranial lesions: up to two lesions per organ representative of all involved organs should be selected as target lesions; the total number of target lesions should not exceed five and all lesions in excess of these five target lesions have to be regarded as non-target lesions.

Baseline Documentation of Intracranial Target and Non-Target Lesions

- All baseline lesion assessments must be performed within 28 days of the first dose of study treatment.
- Measurable and non-measurable intracranial (i.e. brain parenchyma) lesions up to a maximum of 5 lesions should be identified as target lesions, and recorded and measured at baseline. These lesions should be selected on the basis of their size (lesions with the longest diameter) and their suitability for accurate repeated measurements (either by imaging techniques or clinically).
- Cystic lesions thought to represent cystic metastases should not be selected as target lesions when other suitable target lesions are available.
- Measurable intracranial lesions that have been previously irradiated and have not been shown to be progressing following irradiation should not be considered as target

Proprietary Information of MD Anderson

lesions. All other intracranial lesions should be identified as non-target and should also be recorded at baseline. Measurements of non-target lesions are not required, but the presence or absence of each should be noted throughout follow-up.

Baseline Documentation of Extracranial Target and Non-Target Lesions

- All baseline lesion assessments must be performed within 28 days of the first dose of study treatment.
- Lymph nodes that have a short axis of <10mm are considered non-pathological and should not be recorded or followed.
- Pathological lymph nodes with <15mm and ≥10mm short axis are considered non measurable.
- Pathological lymph nodes with ≥15mm short axis are considered measurable and can be selected as target lesions, however lymph nodes should not be selected as target lesions when other suitable target lesions are available.
- Measurable lesions up to a maximum of 2 lesions per organ and 5 lesions in total, representative of all involved extracranial organs, should be identified as target lesions, and recorded and measured at baseline. These lesions should be selected on the basis of their size (lesions with the longest diameter) and their suitability for accurate repeated measurements (either by imaging techniques or clinically).
- Cystic lesions thought to represent cystic metastases should not be selected as target lesions when other suitable target lesions are available.
- Measurable extracranial lesions that have been previously irradiated and have not been shown to be progressing following irradiation should not be considered as target lesions.
- Lytic bone lesions or mixed lytic-blastic lesions, with identifiable soft tissue components, that can be evaluated by CT or MRI can be considered measurable.
- Bone scans, FDG-PET scans or X-rays are not considered adequate imaging techniques to measure bone lesions.
- All other lesions (or sites of disease, excluding the brain) should be identified as non-target and should also be recorded at baseline.
- Non-target lesions will be grouped by organ. Measurements of these lesions are not required, but the presence or absence of each should be noted throughout follow-up.

Overall Intracranial Response - Evaluation of Intracranial Target Lesions

Definitions for assessment of response for intracranial target lesion(s) are as follows:

- Complete Response (CR): Disappearance of all target lesions.
- Partial Response (PR): At least a 30% decrease in the sum of the diameters of target lesions, taking as a reference, the baseline sum of the diameters (e.g. percent change

Proprietary Information of MD Anderson

from baseline).

- Stable Disease (SD): Neither sufficient shrinkage to qualify for PR nor sufficient increase to qualify for progressive disease.
- Progressive Disease (PD): At least a 20% increase in the sum of the diameters of target lesions, taking as a reference, the smallest sum of diameters recorded since the treatment started (e.g. percent change from nadir, where nadir is defined as the smallest sum of diameters recorded since treatment start). In addition, the sum must have an absolute increase from nadir of 5mm.
- Not Evaluable (NE): Cannot be classified by one of the four preceding definitions.

Note: If an intracranial target lesion disappears and reappears at a subsequent time point it should continue to be measured. The response at the time when the lesion reappears will depend upon the status of the other lesions. For example, if the disease had reached a CR status then PD would be documented at the time of reappearance. However, if the response status was PR or SD, the diameter of the reappearing lesion should be added to the remaining diameters and response determined based on percent change from baseline and percent change from nadir.
- Patients, who in the opinion of the treating physician investigator have had a substantial decline in their performance status and have clinical evidence of progressive disease may be classified as having progressive disease.

Proprietary Information of MD Anderson

Appendix 3: Current National Cancer Institute Common Terminology Criteria for Adverse Events (NCI CTCAE Version 4.03)

Please use the following link to the NCI CTCAE website:

http://ctep.cancer.gov/protocolDevelopment/electronic_applications/ctc.htm

Proprietary Information of MD Anderson

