4. MATERIALS AND METHODS

4.1 SUBJECTS

4.1.1 Inclusion Criteria

1. Age \geq 18 years old.
2. Life Expectancy $>$ 12 weeks
3. Subjects must have signed and dated an IRB/IEC approved written informed consent form in accordance with regulatory and institutional guidelines. This must be obtained before the performance of any protocol related procedures that are not part of normal subject care.

Subjects must be willing and able to comply with scheduled visits, treatment schedule, laboratory testing, and other requirements of the study.
4. Histologically confirmed malignant melanoma with measurable metastases in the brain (\geq 0.5 cm)
5. At least one measurable intracranial target lesion, which previously was not treated with local therapy (no prior SRS to this lesion).
 - Largest diameter of \geq 0.5cm, but \leq 3cm as determined by contrast-enhanced MRI
6. Representative formalin-fixed paraffin-embedded (FFPE) tumor specimens in paraffin blocks (blocks are preferred) **OR** at least 4 unstained slides, with an associated pathology report, for testing of tumor PD-L1 expression:
 - Tumor tissue should be of good quality based on total and viable tumor content.
 - Patients who do not have tissue specimens may undergo a biopsy during the screening period. Acceptable samples include core-needle biopsies for deep tumor tissue or excisional, incisional, punch, or forceps biopsies for cutaneous, subcutaneous, or mucosal lesions.
 - Tumor tissue from bone metastases is not evaluable for PD-L1 expression and is therefore not acceptable.
 - However, if repeat biopsy is not feasible, and no archival tissue available patient still may be enrolled.
7. Prior SRT and prior excision of up to 5 MBM is permitted if there has been complete recovery, with no neurologic sequelae, and measurable lesions remain. Growth or change in a lesion previously irradiated will not be considered measurable. Regrowth in cavity of previously excised lesion will not be considered measurable.
 - Any prior SRT to brain lesions or prior excision must have occurred \geq 1 weeks before the start of dosing for this study.
8. Radiation to NON-CNS lesions. Prior radiation to NON-CNS is allowed, and does not require a washout period for treatment initiation.

Proprietary Information of MD Anderson

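### Appendix 2 makes non-measurable brain lesions targets, and by implication admits progressing irradiated ones, against its own 5 mm rule and the eligibility criteria

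*Combined protocol and SAP*

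**What the plan says.** The primary endpoint is the clinical benefit rate (CBR) in the brain: CR, PR, or SD lasting more than 6 months, by modified RECIST 1.1 (Sections 2.1 and 6.1). The brain modifications and the CR, PR and PD definitions, which work on the sum of target-lesion diameters, are in Appendix 2.

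**Size.** The introduction to Appendix 2 says the brain modifications "impact the number and the minimal size of the target lesions selected at baseline". A measurable brain lesion is one that can be "accurately measured in at least one dimension with the longest diameter ≥ 5 mm when evaluated with contrast-enhanced MRI". The list for baseline documentation of intracranial lesions then says: "Measurable and non-measurable intracranial (i.e. brain parenchyma) lesions up to a maximum of 5 lesions should be identified as target lesions". The extracranial list in the same appendix restricts targets to measurable lesions.

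**Cystic lesions.** The opening paragraph of Appendix 2 counts cystic lesions as non-measurable. The baseline list says only: "Cystic lesions thought to represent cystic metastases should not be selected as target lesions when other suitable target lesions are available".

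**Irradiated lesions.** Appendix 2 says: "Measurable intracranial lesions that have been previously irradiated and have not been shown to be progressing following irradiation should not be considered as target" lesions. Section 4.1.1, inclusion criterion 7, says: "Growth or change in a lesion previously irradiated will not be considered measurable". The note to exclusion criterion 2 (Section 4.1.2) requires the earlier stereotactic field to have left out the brain index lesions.

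**Guaranteed lesion.** Inclusion criteria 4 and 5 require at least one measurable brain target lesion of 0.5 cm or more with no earlier local therapy.

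**The concern.** If non-measurable lesions can be targets, the 5 mm minimum does nothing at baseline. Two readers could each follow Appendix 2, one from its introduction and one from its baseline list, and build different sums for the same scan. Irradiated lesions raise the same problem: Appendix 2 leaves a progressing one in the pool of possible targets, while Section 4.1.1 says its growth is not measurable.

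Percentage change in the target sum decides PR and PD, and so feeds the primary endpoint. Small lesions weigh heavily when the measurable lesion is itself small. PD needs an absolute rise of 5 mm as well as 20%; PR has no absolute floor. In a cohort of 25, one reclassified patient is 1/25 = 4 percentage points of CBR.

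**Working it through.** **1. The plan's own figure.** Section 6.1 gives 84% power for n = 25, 16% against 35%, one-sided 0.10. With the one-sample score test:

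Φ[(√25 × (0.35 − 0.16) − 1.2816 × √(0.16 × 0.84)) / √(0.35 × 0.65)] = Φ[(0.950 − 0.470) / 0.477] = Φ(1.007) = 0.843.

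The figure reproduces. It does not depend on which lesions are targets and is not in dispute.

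**2. The texts side by side.**

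| Question | One place | Another place |
|---|---|---|
| Can a brain lesion under 5 mm be a target? | No: a minimal target size applies (Appendix 2, introduction) | Yes: non-measurable lesions are named (Appendix 2, baseline list) |
| Can a cystic lesion be a target? | It is non-measurable (Appendix 2, opening) | Yes, if no other suitable lesion exists (baseline list) |
| Can a progressing irradiated lesion be a target? | Not barred (Appendix 2, baseline list) | Its growth is not measurable (inclusion 7); index lesions lie outside the earlier field (note to exclusion 2) |

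The first row is an explicit instruction against an explicit rule. In the third, permission follows only by implication.

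**3. What it can do to a patient's category.** The diameters are assumed. Baseline: one measurable lesion of 6 mm and four lesions of 4 mm. The sum is 6 + 4 × 4 = 22 mm, of which 16/22 = 73% is non-measurable.

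| Follow-up | All five as targets | Measurable lesion only |
|---|---|---|
| 6 mm unchanged; four shrink to 2 mm | 22 → 14 mm, −8/22 = −36.4%: PR | 6 → 6 mm, 0%: SD |
| 6 mm unchanged; four grow to 6, 5, 5, 5 mm | 22 → 27 mm, +5/22 = +22.7% and +5 mm: PD | 6 → 6 mm, 0%: SD |
| 6 mm disappears; four unchanged | 22 → 16 mm, −6/22 = −27.3%: SD | 6 → 0 mm, −100%: target-lesion CR |

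The error runs in both directions.

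**4. From category to CBR.** I read the 6-month condition as attached to SD alone.
- SD to PD: can change CBR directly, by ending stable disease before 6 months.
- SD to PR, or the reverse: changes CBR only if disease control ends at or before 6 months. Otherwise the patient counts as benefiting either way.

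**5. Scale for 25 patients.** The plan states no success cut-off. An exact binomial rule of at least 7 of 25 gives type I error 0.092 and power 0.827. If misclassification raised the null rate by 4 points (16% to 20%), the chance of passing would be 0.220. If it lowered the alternative by 4 points (35% to 31%), power would be 0.698. The 4-point shift is an assumption used only to show what one patient is worth.

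**The case against.** Much of the case for leaving the text alone is fair.

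- Appendix 2 selects targets by longest diameter and by suitability for accurate repeat measurement, so lesions under 5 mm would enter only when fewer than five larger suitable ones exist. This stands. It limits how often the problem arises but does not override a sentence that names non-measurable lesions.
- Inclusion criteria 4 and 5 guarantee a measurable, untreated lesion. A reader might infer that the brain sum could consist only of lesions the protocol calls non-measurable. In an eligible subject whose qualifying lesion is selected, it cannot.
- A reader might also infer that Appendix 2 instructs selection of irradiated lesions, or that inclusion 5 forbids them. Neither is right. Appendix 2 merely fails to bar progressing ones, and inclusion 5 asks for at least one untreated target without excluding irradiated lesions as additional targets. The tension is with inclusion 7, which concerns measurability, and with the note to exclusion 2.
- Growth of small non-target lesions may be called progression anyway: the RANO table in Appendix 1 counts unequivocal non-target progression as PD. This weakens the PD example where growth is judged unequivocal, but a judgement on non-target lesions is not the same as a 20% and 5 mm rule.
- Section 3 assigns the primary response endpoint to central review under RECIST 1.1, while Sections 2.1 and 6.1 name the modified criteria. How far Appendix 2 drives the primary result depends on which governs. That needs settling, but it does not reconcile Appendix 2 with itself.

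**Conclusion.** The point holds. On size, Appendix 2 contradicts its own minimum and its own extracranial rule. On irradiated lesions, its wording by implication admits progressing ones, out of line with inclusion 7 and the note to exclusion 2. On cystic lesions, it calls them non-measurable yet allows them conditionally as targets.

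The consequence is possible misclassification of individual patients. Under the assumed diameters, non-measurable lesions make up 73% of the baseline sum and move a patient from SD to PR or from SD to PD. The documents give neither lesion-size distributions nor durations of control, so the net effect on CBR cannot be estimated.

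A reader might infer that the rule inflates CBR in the drug's favour. The documents do not support that: it can also produce a false PD or hide a response, and nothing in them shows late radiation effects being scored as drug response. Sample size and stated power are unaffected. The fault should be corrected because it touches the primary endpoint and the correction is nearly free.

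**What to change.** In Appendix 2, intracranial baseline list:

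1. Delete the words *and non-measurable*, so that brain targets are up to five lesions of at least 5 mm on contrast-enhanced MRI. Smaller lesions are recorded as non-target.
2. In the irradiated-lesion bullet, delete only the clause about not having been shown to progress after irradiation, so that previously irradiated brain lesions are not targets, in line with inclusion 7 and the note to exclusion 2. Keep the sentence that follows, which makes all other intracranial lesions non-target and has them recorded at baseline; replacing the whole bullet would lose it.
3. Reconcile the cystic-lesion bullet with the opening paragraph of Appendix 2, which treats cystic lesions as non-measurable.

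The cost is a short wording amendment. It needs no extra scans, visits or patients, and n = 25 with 84% power is unchanged. If subjects are already enrolled, their baseline target lists should be checked against the single rule and any re-selection documented before CBR is analysed.

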There is no optimal systemic or local therapy for melanoma metastatic to the brain. Therapy for small, single lesions or a limited number of metastases consists of surgery or stereotactic radiotherapy (SRT), with a moderate local control rate but a high incidence of new lesions that are neither prevented by nor responsive to whole brain radiation. Temozolomide, a drug with very high CNS penetration, has been studied in this setting but has a response rate of <10% in both the CNS and overall, so it contributes little benefit and has no apparent synergy with radiotherapy [6], [9], [10], [11]. Combining any of these approaches with whole brain irradiation has been of little value in the management of these subjects [12]. While antibodies are not believed to cross an intact blood-brain barrier, activated T-cells may be able to penetrate the blood brain barrier, providing a rationale for testing immunomodulatory therapies in this setting [13], [14]. Previously reported results from the Phase 2 study (CA184042) of ipilimumab monotherapy showed similar clinical benefit in the brain and systemically, with durable disease control of 24% (CNS) and 27% (extra-cranial) of these patients, providing a rationale for further study of promising immunotherapies in melanoma patients with brain metastases [15].

Similarly, ipilimumab combined with fotemustine was associated with a disease control rate (complete response [CR] + partial response [PR] + stable disease [SD]) of 50% (10/20) in patients with asymptomatic brain metastases in a Phase 2 trial (NIBIT-M1) [16]. In a Phase 1 dose escalation study (CA209004), the combination of nivolumab and ipilimumab was studied in subjects with unresectable or metastatic melanoma. An objective response rate of 53% was observed when patients were treated with the combination regimen (ipilimumab 3 mg/kg + nivolumab 1 mg/kg every 3 weeks x 4); an additional benefit of prolonged stable disease or minor response occurred in another ~20% of patients [17]. Since brain metastases in melanoma are the most frequent cause of death from this disease and the brain is a frequent site of failure even in subjects who achieve control of extra-cranial disease with systemic therapy, it is essential to discover whether the combination of ipilimumab plus pembrolizumab can provide similar promise to patients whose melanoma has metastasized to the brain.

Proprietary Information of MD Anderson

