2 OBJECTIVES

2.1 PRIMARY OBJECTIVE

To assess clinical benefit rate (CBR), defined as CR + PR + SD > 6 months, in the brain in subjects with MBM per modified RECIST 1.1 criteria who are treatment naïve to anti-PD-1 agents in the metastatic setting (prior adjuvant anti-PD1 allowed. See inclusion and exclusion criteria).

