6.1 SAMPLE SIZE JUSTIFICATION

The primary objective of the study is to assess CBR, defined as CR + PR + SD > 6 months, in the brain in subjects with MBM per modified RECIST 1.1 criteria who are treatment naïve to anti-PD-1 agents in the metastatic setting (Cohort A). A sample size of 25 subjects will achieve 84% power to detect a difference of 19% (anticipated CBR of 35% - 16% [historical control]) using a chi-squared test at a one-sided significance level of 0.10 (nQuery Advisor® 7.0). For Cohort B, assuming a CBR of 20% for patients who previously progressed on PD-1 inhibitors, the probability of observing at least one subject experiencing clinical benefit out of 5 subjects is 0.67.

Reference

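### The plan gives conflicting answers on how new and non-target brain lesions count in the primary brain clinical benefit rate

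*Combined protocol and SAP*

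**What the plan says.** Section 2.1 makes brain CBR by modified RECIST 1.1 the primary aim, counting CR, PR and SD that lasts beyond 6 months, in patients naïve to anti-PD-1 agents in the metastatic setting (Cohort A). Section 6.1 repeats it and sizes the cohort: "A sample size of 25 subjects will achieve 84% power to detect a difference of 19" percentage points, 35% against a historical 16%, at one-sided 0.10. Section 6.2.1 plans an estimate with an exact 95% confidence interval and states no success threshold.

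Four pieces of text bear on how brain lesions other than targets are scored:

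- **Appendix 2, opening.** Intracranial response and progression follow RECIST v1.1. The modifications are said to affect only how many target lesions are chosen and how small they may be. Beyond five targets, "all brain lesions in excess of these five target lesions have to be regarded as non-target lesions". The presence or absence of non-target lesions is to be noted during follow-up.
- **Appendix 2, Overall Intracranial Response.** CR is given as "Complete Response (CR): Disappearance of all target lesions", and PR, SD and PD are defined on the target-lesion sum. No non-target category, new-lesion rule or combining rule follows. The only other route to PD is a discretionary one for clinical decline.
- **Appendix 1, brain-metastasis table.** CR and PR require that there be no new lesions. PD includes "or unequivocal progression of enhancing non-target lesions; or new lesions; or substantial clinical decline".
- **Appendix 1, iRANO note.** "The appearance of new lesions 6 months or less from the initiation of immunotherapy alone does not define progressive disease". The note also recommends confirmatory imaging 3 months after early radiographic progression in patients without new or substantially worse neurological deficit. Confirmed progression is dated back to its first appearance.

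The criteria set itself varies. Sections 2.1, 4.4.13 and 6.1 use modified RECIST 1.1. Section 3 uses RECIST 1.1 by central review for the primary response endpoint, and also RANO-BM for brain MRI. Section 4.4.6 uses RECIST 1.1 together with RANO-BM.

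**The concern.** A brain CBR has to say what happens when the measured lesions are controlled but the brain is not. This is not a rare corner of the disease: Section 1.1.1 reports "a high incidence of new lesions" after surgery or stereotactic radiotherapy. Two of the four texts, read literally, let a patient with new brain metastases count as clinical benefit, and one of those also passes over non-target growth. The other two point towards the opposite answer.

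Compared with scoring these events as progression, the lenient readings can add successes but never remove them. With 25 patients and a single-arm comparison against a fixed 16%, a few such patients would matter. If the choice of rule is left until scans have been read, it may also be made with the results in view.

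**Working it through.** **1. The plan's own figure.** Inputs from Section 6.1: n = 25, p0 = 0.16, p1 = 0.35, one-sided alpha 0.10 (z = 1.2816). One-sample normal approximation:

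power = Φ[(0.19 × √25 − 1.2816 × √(0.16 × 0.84)) / √(0.35 × 0.65)] = Φ[(0.950 − 0.470) / 0.477] = Φ(1.007) = 0.843.

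This reproduces the stated 84%. No printed figure is wrong on this point.

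**2. Two patients scored under each text.** Patient X has a target sum down by at least 30% and a new, asymptomatic brain lesion on the week 6 MRI. Patient Y has stable targets beyond 6 months, with unequivocal growth of a non-target brain lesion within that time.

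| Text applied | Patient X | Patient Y |
|---|---|---|
| Appendix 2 written categories, taken as overall response | PR: benefit | SD > 6 months: benefit |
| Appendix 2 opening (RECIST v1.1 kept except target number and size) | Parent rules on new lesions retained but not reproduced | Parent rules on non-target lesions retained but not reproduced |
| Appendix 1 table | PD | PD |
| Appendix 1 table with iRANO note | Not CR or PR (new lesion); not PD on that ground alone; SD by default, unless progression is confirmed and back-dated | New-lesion sentence does not apply; progression remains subject to confirmation and back-dating |

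The definitions written out in the plan therefore give opposite primary-endpoint results for both patients.

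**3. Effect of back-dating.** Suppose a new lesion appears at month 4 and progression is confirmed 3 months later, at month 7. Under the note, progression is dated to month 4 and SD > 6 months fails. That protection works only if the note governs CBR, if a persisting new lesion counts as confirmation, and if back-dating is done before the 6-month criterion is judged. The plan states none of these three.

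**4. Size per patient.** 1/25 = 4 percentage points of Cohort A CBR.

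**5. Hypothetical effect on a false positive.** The plan gives neither a success threshold nor a rate of such patients, so both are assumed here. The smallest count with exact one-sided alpha at or below 0.10 is 7 of 25: P(X ≥ 7 | 0.16) = 0.092, while 6 of 25 gives 0.200. Exact power at 7 is 0.827. Take true CBR as 16% when new and non-target progression count as PD, and add an assumed share of all patients scored as benefit under the lenient reading:

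| Assumed added share | Apparent CBR | P(X ≥ 7 of 25) |
|---|---|---|
| 0 | 16% | 0.092 |
| 4% (1 of 25) | 20% | 0.220 |
| 10% | 26% | 0.485 |
| 20% (5 of 25) | 36% | 0.852 |

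Expressed instead as a share m of true non-benefit patients, apparent CBR is 0.16 + 0.84m. Then m = 5% gives 20.2% and a probability of 0.228; m = 10% gives 24.4% and 0.411. These figures show sensitivity only and are not predictions.

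**The case against.** The strongest reply is that this is an incomplete write-up, and much of that stands. The opening of Appendix 2 keeps the RECIST v1.1 definitions and confines the modifications to the number and size of targets, so nothing says that the parent rules on new and non-target lesions are dropped. The line under the heading describes the categories as applying to target lesions. A trained reader would probably supply the missing step.

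That reply does not remove the conflict. The heading calls the result overall intracranial response, and no overall rule follows. Section 3 says RECIST 1.1 is further adapted for tumour flare as described in Section 4, but Section 4 contains no new-lesion scoring rule. Section 4.2.4 does add another change, excluding lesions treated with stereotactic radiotherapy from the sum. The phrase modified RECIST 1.1 therefore does not tell a reader which parent rules survive.

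Stronger readings are tempting, and the documents do not support them:

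- *That the protocol deliberately scores the primary endpoint on target lesions alone.* The Appendix 2 opening and the Appendix 1 table both point the other way.
- *That the iRANO note exempts new lesions throughout the window in which SD > 6 months is earned.* Nothing says the note governs CBR. It concerns new lesions alone, does not excuse non-target growth, and comes with confirmation and back-dating.
- *That PFS is biased as well.* Section 6.2.2 defines PFS by progression or death and does not link it to the target-only categories.
- *That the result cannot be compared with the 16% control.* Section 6.1 does not say how that control scored new lesions.

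**Conclusion.** The conflict is real and affects who counts as a success in the primary endpoint, so it is more than a missing detail. The plan contains text under which a patient with new brain metastases is a clinical benefit and text under which the same patient has progressed. For non-target growth, the conflict is between the Appendix 2 categories read literally and the Appendix 1 table.

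Relative to counting these events as progression, any error goes one way, upward, at 4 percentage points per Cohort A patient. How many patients would be affected cannot be derived from the documents. The probabilities in the working rest on assumed shares, on a true CBR of 16% and on a 7-of-25 threshold that the plan does not state. They should not be quoted as the trial's false-positive rate. The 84% power calculation is unaffected.

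**What to change.** In Appendix 2:

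- Relabel the existing CR, PR, SD and PD definitions as target-lesion response.
- Add an overall intracranial response rule for CBR that combines target, non-target and new brain lesions, in line with the appendix's own opening and the Appendix 1 table. CR and PR would require no new brain lesion. An unequivocal new brain lesion, or unequivocal non-target progression, would be PD.

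In Appendix 1, state whether the iRANO note applies to endpoint scoring or only to treatment decisions. If it applies to scoring, say what confirms progression when the first sign is a new lesion, and that confirmed progression is back-dated before SD > 6 months is judged.

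Name one criteria set for the primary endpoint and use it in Sections 2.1, 3, 4.4.6, 4.4.13 and 6.1.

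The rules for continuing treatment after progression are a separate matter. The sponsor should check them for consistency with the scoring rule, and no change to them is proposed here.

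The cost is wording only. The planned MRIs already provide the information, and the sample size does not change. Observed CBR may be slightly lower than under the lenient readings. The change should be made before scans are scored for the endpoint.
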